3.0260	All Treated	OVT1B	Summary of Changes in Temperature from Baseline (Part 1)	Report for: Part 1, (Summarize: by ascending dose level, Total). Include only 'worst-case post-baseline'	SAC [A]
3.0261	All Treated	OVT1B	Summary of Changes in Temperature from Baseline (Part 2 MM)	Report for: Part 2 MM, (Summarize: only for 3.4 MM) Include only 'worst-case post-baseline'	SAC [A]
3.0262	All Treated	OVT1B	Summary of Changes in Temperature from Baseline (All Treated MM)	Report for: All Treated MM, (Summarize: Total). Include only 'worst-case post-baseline'	SAC [A]
3.0263	All Treated	OVT1B	Summary of Changes in Temperature from Baseline (Part 2 NHL)	Report for: Part 2 NHL, (Summarize: only for 3.4 NHL) Include only 'worst-case post-baseline'	SAC
ECOG Performance Status					
3.0410	All Treated	PS1A	Summary of ECOG Performance Status (Part 1)	Report for: Part 1, (Summarize: by ascending dose level, Total).	SAC [A]
3.0411	All Treated	PS1A	Summary of ECOG Performance Status (Part 2 MM)	Report for: Part 2 MM, (Summarize: only for 3.4 MM)	SAC [A]
3.0412	All Treated	PS1A	Summary of ECOG Performance Status (All Treated MM)	Report for: All Treated MM, (Summarize: Total).	SAC [A]

Safety: Tables					
No.	Population	IDSL / Example Shell	Title	Programming Notes	Deliverable [Priority]
3.0413	All Treated	PS1A	Summary of ECOG Performance Status (Part 2 NHL)	Report for: Part 2 NHL, (Summarize: only for 3.4 NHL)	SAC
3.0420	All Treated	PS3A	Summary of Change in ECOG Performance Status from Baseline (Part 1)	Report for: Part 1, (Summarize: by ascending dose level, Total).	SAC [A]
3.0421	All Treated	PS3A	Summary of Change in ECOG Performance Status from Baseline (Part 2 MM)	Report for: Part 2 MM, (Summarize: only for 3.4 MM)	SAC [A]
3.0422	All Treated	PS3A	Summary of Change in ECOG Performance Status from Baseline (All Treated MM)	Report for: All Treated MM, (Summarize: Total).	SAC [A]
3.0423	All Treated	PS3A	Summary of Change in ECOG Performance Status from Baseline (Part 2 NHL)	Report for: Part 2 NHL, (Summarize: only for 3.4 NHL)	SAC
Left Ventricular Ejection Fraction					
3.0480	All Treated	OLVEF1 A	Summary of Left Ventricular Ejection Fraction Change from Baseline (Part 1)	Report for: Part 1, (Summarize: by ascending dose level, Total). Footnote: LLN: Normal Range Lower Limit.	SAC [A]
3.0481	All Treated	OLVEF1 A	Summary of Left Ventricular Ejection Fraction Change from Baseline (Part 2 MM)	Report for: Part 2 MM, (Summarize: only for 3.4 MM). Footnote: LLN: Normal Range Lower Limit.	SAC [A]
3.0482	All Treated	OLVEF1 A	Summary of Left Ventricular Ejection Fraction Change from Baseline (All Treated MM)	Report for: All Treated MM, (Summarize: Total). Footnote: LLN: Normal Range Lower Limit.	SAC [A]
3.0483	All Treated	OLVEF1 A	Summary of Left Ventricular Ejection Fraction Change from Baseline (Part 2 NHL)	Report for: Part 2 NHL, (Summarize: only for 3.4 NHL)	SAC

CONFIDENTIAL

BMA117159

Safety: Tables					
No.	Population	IDSL / Example Shell	Title	Programming Notes	Deliverable [Priority]
Ocular Exams					
3.0490	All Treated	SAFE_T 1	Summary of Subjects Experiencing Corneal Clinical Signs (Part 1)	Report for: Part 1, (Summarize: by ascending dose level, Total).	SAC [A]
3.0491	All Treated	SAFE_T 1	Summary of Subjects Experiencing Corneal Clinical Signs (Part 2 MM)	Report for: Part 2 MM, (Summarize: only for 3.4 MM)	SAC [A]
3.0492	All Treated	SAFE_T 1	Summary of Subjects Experiencing Corneal Clinical Signs (All Treated MM)	Report for: All Treated MM, (Summarize: Total).	SAC [A]
3.0493	All Treated	SAFE_T 1	Summary of Subjects Experiencing Corneal Clinical Signs (Part 2 NHL)	Report for: Part 2 NHL, (Summarize: only for 3.4 NHL)	SAC
3.0500	All Treated	SAFE_T 2	Summary of Best Corrected Visual Acuity Test (BCVA) Scores (logMAR score) (Part 1)	Report for: Part 1, (Summarize: by ascending dose level, Total).	SAC [A]
3.0501	All Treated	SAFE_T 2	Summary of Best Corrected Visual Acuity Test (BCVA) Scores (logMAR score) (Part 2 MM)	Report for: Part 2 MM, (Summarize: only for 3.4 MM)	SAC [A]
3.0502	All Treated	SAFE_T 2	Summary of Best Corrected Visual Acuity Test (BCVA) Scores (logMAR score) (All Treated MM)	Report for: All Treated MM, (Summarize: Total).	SAC [A]
3.0503	All Treated	SAFE_T 2	Summary of Best Corrected Visual Acuity Test (BCVA) Scores (logMAR score) (Part 2 NHL)	Report for: Part 2 NHL, (Summarize: only for 3.4 NHL)	SAC
Death					
3.0570	All Treated	DTH1a	Summary of Deaths (Part 1)	Report for: Part 1, (Summarize: by ascending dose level, Total).	SAC [A]
3.0571	All Treated	DTH1a	Summary of Deaths (Part 2 MM)	Report for: Part 2 MM, (Summarize: only for 3.4 MM)	SAC [A]
3.0572	All Treated	DTH1a	Summary of Deaths (All Treated MM)	Report for: All Treated MM, (Summarize: Total).	SAC [A]

CONFIDENTIAL

BMA117159

Safety: Tables					
No.	Population	IDSL / Example Shell	Title	Programming Notes	Deliverable [Priority]
3.0573	All Treated	DTH1a	Summary of Deaths (Part 2 NHL)	Report for: Part 2 NHL, (Summarize: only for 3.4 NHL)	SAC
Constitutional B- Symptoms					
3.0813	All Treated	OCS1	Summary of Constitutional Symptoms over Time (Part 2 NHL)	Report for: Part 2 NHL, (Summarize: only for 3.4 NHL)	SAC
Organ Examination					
3.0823	All Treated	OOE1	Summary of Organ Examination over Time (Part 2 NHL)	Report for: Part 2 NHL, (Summarize: only for 3.4 NHL)	SAC
Health Outcome					
3.0830	All Treated	SAFE_T 3	Summary of Symptom Impact and HRQoL Item Scores (Part 1)	Report for: Part 1, (Summarize: by ascending dose level, Total).	SAC [A]
3.0831	All Treated	SAFE_T 3	Summary of Symptom Impact and HRQoL Item Scores (Part 2 MM)	Report for: Part 2 MM, (Summarize: only for 3.4 MM)	SAC [A]
3.0832	All Treated	SAFE_T 3	Summary of Symptom Impact and HRQoL Item Scores (All Treated MM)	Report for: All Treated MM, (Summarize: Total).	SAC [A]
3.0833	All Treated	SAFE_T 3	Summary of Symptom Impact and HRQoL Item Scores (Part 2 NHL)	Report for: Part 2 NHL, (Summarize: only for 3.4 NHL)	SAC

CONFIDENTIAL

BMA117159

Safety: Tables					
No.	Population	IDSL / Example Shell	Title	Programming Notes	Deliverable [Priority]
Anti-Drug Antibody					
3.0840	All Treated	SAFE_T 4	Summary of Human Anti-GSK2857916 Antibodies (ADA) Over Time (Part 1)	Report for: Part 1, (Summarize: by ascending dose level, Total).	SAC [A]
3.0841	All Treated	SAFE_T 4	Summary of Human Anti-GSK2857916 Antibodies (ADA) Over Time (Part 2 MM)	Report for: Part 2 MM, (Summarize: only for 3.4 MM)	SAC [A]
3.0842	All Treated	SAFE_T 4	Summary of Human Anti-GSK2857916 Antibodies (ADA) Over Time (All Treated MM)	Report for: All Treated MM, (Summarize: Total).	SAC [A]
3.0843	All Treated	SAFE_T 4	Summary of Human Anti-GSK2857916 Antibodies (ADA) Over Time (Part 2 NHL)	Report for: Part 2 NHL, (Summarize: only for 3.4 NHL)	SAC
3.0850	All Treated	SAFE_T 5	Summary of Anti-GSK2857916 Antibodies (ADA) (Part 1)	Report for: Part 1, (Summarize: by ascending dose level, Total).	SAC [A]
3.0851	All Treated	SAFE_T 5	Summary of Anti-GSK2857916 Antibodies (ADA) (Part 2 MM)	Report for: Part 2 MM, (Summarize: only for 3.4 MM)	SAC [A]
3.0852	All Treated	SAFE_T 5	Summary of Anti-GSK2857916 Antibodies (ADA) (All Treated MM)	Report for: All Treated MM, (Summarize: Total).	SAC [A]
3.0853	All Treated	SAFE_T 5	Summary of Anti-GSK2857916 Antibodies (ADA) (Part 2 NHL)	Report for: Part 2 NHL, (Summarize: only for 3.4 NHL)	SAC

NOTES:

A. Indicates which displays will be generated for the reporting effort for multiple myeloma

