4.1.4. Safety Tables

Safety: Tables					
No.	Population	IDSL / Example Shell	Title	Programming Notes	Deliverable [Priority]
Adverse Events (AEs)					
3.0030	All Treated	OAE01	Summary of All Adverse Events by System Organ Class and Preferred Term and Maximum Grade (Part 1)	Report for: Part 1, (Summarize: by ascending dose level, Total).	EOS SAC
3.0031	All Treated	OAE01	Summary of All Adverse Events by System Organ Class and Preferred Term and Maximum Grade (Part 2 MM)	Report for: Part 2 MM, (Summarize: only for 3.4 MM).	EOS SAC
3.0033	All Treated	OAE01	Summary of All Adverse Events by System Organ Class and Preferred Term and Maximum Grade (Part 2 NHL)	Report for: Part 2 NHL, (Summarize: only for 3.4 NHL)	EOS SAC
3.0793	All Treated	AE3	Summary of Common ($\geq 5\%$) Grade 2-4 Adverse Events by Overall Frequency (Part 2 NHL)	Report for: Part 2 NHL, (Summarize: only for 3.4 NHL)	EOS SAC
3.0060	All Treated	OAE01	Summary of All Drug-Related Adverse Events by System Organ Class and Preferred Term and Maximum Grade (Part 1)	Report for: Part 1, (Summarize: by ascending dose level, Total).	EOS SAC
3.0061	All Treated	OAE01	Summary of All Drug-Related Adverse Events by System Organ Class and Preferred Term and Maximum Grade (Part 2 MM)	Report for: Part 2 MM, (Summarize: only for 3.4 MM).	EOS SAC
3.0063	All Treated	OAE01	Summary of All Drug-Related Adverse Events by System Organ Class and Preferred Term and Maximum Grade (Part 2 NHL)	Report for: Part 2 NHL, (Summarize: only for 3.4 NHL)	EOS SAC
3.0693	All Treated	AE15	Summary of Common ($\geq 5\%$) Non-serious Adverse Events by System Organ Class and Preferred Term (Number of Participants and Occurrences) (Part 2 NHL)	Report for: Part 2 NHL, (Summarize for Total). Include baseline values.	EOS SAC
3.0713	All Treated	AE3	Summary of Common ($\geq 5\%$) Drug-Related Grade 2-4 Adverse Events by Overall Frequency (Part 2 NHL)	Report for: Part 2 NHL, (Summarize for Total). Include baseline values.	EOS SAC
3.0700	All Treated	AE16	Summary of Serious Adverse Events by System Organ Class and Preferred Term (Number of Participants and Occurrences) (Part 1)	Report for: Part 1, (Summarize by ascending dose level, Total).	EOS SAC

CONFIDENTIAL

BMA117159

Safety: Tables					
No.	Population	IDSL / Example Shell	Title	Programming Notes	Deliverable [Priority]

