2.3. Study Design

Overview of Study Design and Key Features	

Design Features
	
 • Part 1 Dose Escalation 
 ○ Population: Subjects with relapsed/refractory MM (originally planned to enrol up to 30 subjects. However, additional subjects were enrolled to explore a new intermediate dose group) ○ Objective: characterize safety, PK, PD, immunogenicity and establish RP2 dose of GSK2857916 ○ Two dosing schedules (Schedule 1 and Schedule 2) may be explored: 
 ▪ Schedule 1: GSK2587916 once every 3 weeks (21-day cycle) (n~20) ▪ Schedule 2: GSK2587916 once weekly for 3 consecutive weeks, 1-week rest (28-day cycle) (n~9). Schedule 2 was not actually explored. ○ Serial PK samples will be collected from all subjects in Part 1 • Part 2 Expansion Cohort(s) (n~50 subjects) 
 ○ Population: 
 ▪ Subjects with relapsed/refractory MM (up to 40 subjects) ▪ Subjects with lymphomas expressing BCMA (up to 10 subjects) ○ Objective: Further evaluate the safety, PK, immunogenicity, and clinical activity of GSK2857916 at the RP2 dose identified in Part 1 ○ MM and Lymphoma expansion cohorts will be analyzed separately ○ Sparse PK samples will be collected from all subjects • Genetics research samples will be collected predose from all subjects

Overview of Study Design and Key Features	
Dosing	
 • Part 1 Dose Escalation Initially, GSK2857916 will be administered (IV) via 60 min infusion once every three weeks (21 days = 1 cycle) on Schedule 1. Once an MTD1 or RP2D has been established on the once every 21-day (Schedule 1), the safety, tolerability, PK, and PD of once-weekly dosing (Schedule 2) of GSK2857916 may be explored as an additional cohort(s). • Part 2: Dose Expansion Phase Subjects enrolled in Part 2 dose expansion phase will be administered GSK2857916 at recommended phase 2 dose (RP2D) established based on Part 1 outcomes.
Time & Events	
 • Refer to Appendix 2: Schedule of Activities
Treatment Assignment	
 • This is a non-randomized open-label study.

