8.1. Adverse Events Analyses

Adverse events analyses including the analysis of adverse events (AEs), Serious (SAEs) and other significant AEs will be based on GSK Core Data Standards. The details of the planned displays are provided in [Appendix 12: List of Data Displays](#).

An overview summary of AEs, including counts and percentages of subjects with any AE, AEs related to study treatment, AEs leading to permanent discontinuation of study treatment, AE leading to dose reductions, AEs leading to dose delays OR interruptions, SAEs, SAEs related to study treatment, fatal SAEs, and fatal SAEs related to study treatment will be produced.

A summary of non-serious AEs that occurred in strictly 5% of the subjects or above will be provided (no rounding for the percentage will be used in terms of 5% threshold, e.g., event with 4.9% incidence rate should not be included in this table). The summary will be displayed by SOC and PT.

The relationship between MedDRA SOC, PT, and Verbatim Text will be displayed.

Adverse events (AEs) will be graded according to the CTCAE, Version 4.0. Adverse events will be coded to the preferred term (PT) level using the Medical Dictionary for Regulatory Affairs (MedDRA dictionary).

A summary of number and percentage of subjects with any adverse events by maximum grade will be produced. AEs will be sorted by Preferred term (PT) in descending order of total incidence. The summary will use the following algorithms for counting the subject:

- **Preferred term row:** Subjects experiencing the same AE preferred term several times with different grades will only be counted once with the maximum grade.
- **Any event row:** Each subject with at least one adverse event will be counted only once at the maximum grade no matter how many events they have.

In addition, the frequency and percentage of AEs (all grades) will be summarized and displayed in two ways: 1) in descending order of total incidence by PT only and 2) in descending order of total incidence by System Organ Classes (SOC) and PT and Maximum Grade. In the SOC row, the number of subjects with multiple events under the same system organ class will be counted once.

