3.0780	All Treated	AE3	Summary of Common (>=5%) Adverse Events by Overall Frequency (Part 1)	Report for: Part 1, (Summarize: by ascending dose level, Total).	SAC [A]
3.0781	All Treated	AE3	Summary of Common (>=5%) Adverse Events by Overall Frequency (Part 2 MM)	Report for: Part 2 MM, (Summarize: only for 3.4 MM)	SAC [A]
3.0782	All Treated	AE3	Summary of Common (>=5%) Adverse Events by Overall Frequency (All Treated MM)	Report for: All Treated MM, (Summarize: Total).	SAC [A]
3.0783	All Treated	AE3	Summary of Common (>=5%) Adverse Events by Overall Frequency (Part 2 NHL)	Report for: Part 2 NHL, (Summarize: only for 3.4 NHL)	SAC
3.0790	All Treated	AE3	Summary of Common (>=5%) Grade 2-4 Adverse Events by Overall Frequency (Part 1)	Report for: Part 1, (Summarize: by ascending dose level, Total).	SAC [A]
3.0791	All Treated	AE3	Summary of Common (>=5%) Grade 2-4 Adverse Events by Overall Frequency (Part 2 MM)	Report for: Part 2 MM, (Summarize: only for 3.4 MM)	SAC [A]
3.0792	All Treated	AE3	Summary of Common (>=5%) Grade 2-4 Adverse Events by Overall Frequency (All Treated MM)	Report for: All Treated MM, (Summarize: Total).	SAC [A]
3.0793	All Treated	AE3	Summary of Common (>=5%) Grade 2-4 Adverse Events by Overall Frequency (Part 2 NHL)	Report for: Part 2 NHL, (Summarize: only for 3.4 NHL)	SAC
3.0060	All Treated	OAE01	Summary of All Drug-Related Adverse Events by System Organ Class and Preferred Term and Maximum Grade (Part 1)	Report for: Part 1, (Summarize: by ascending dose level, Total).	SAC [A]

CONFIDENTIAL

BMA117159

Safety: Tables					
No.	Population	IDSL / Example Shell	Title	Programming Notes	Deliverable [Priority]
3.0061	All Treated	OAE01	Summary of All Drug-Related Adverse Events by System Organ Class and Preferred Term and Maximum Grade (Part 2 MM)	Report for: Part 2 MM, (Summarize: only for 3.4 MM)	SAC [A]
3.0062	All Treated	OAE01	Summary of All Drug-Related Adverse Events by System Organ Class and Preferred Term and Maximum Grade (All Treated MM)	Report for: All Treated MM, (Summarize: Total).	SAC [A]
3.0063	All Treated	OAE01	Summary of All Drug-Related Adverse Events by System Organ Class and Preferred Term and Maximum Grade (Part 2 NHL)	Report for: Part 2 NHL, (Summarize: only for 3.4 NHL)	SAC
3.0690	All Treated	AE15	Summary of Common (>=5%) Non-serious Adverse Events by System Organ Class and Preferred Term (Number of Participants and Occurrences) (Part 1)	Report for: Part 1, (Summarize by ascending dose level, Total).	SAC [A]

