3.0691	All Treated	AE15	Summary of Common (>=5%) Non-serious Adverse Events by System Organ Class and Preferred Term (Number of Participants and Occurrences) (Part 2 MM)	Report for: Part 2 MM, (Summarize: only for 3.4 MM).	SAC [A]
3.0692	All Treated	AE15	Summary of Common (>=5%) Non-serious Adverse Events by System Organ Class and Preferred Term (Number of Participants and Occurrences) (All Treated MM)	Report for: All Treated MM, (Summarize for Total). Include baseline values.	SAC [A]
3.0693	All Treated	AE15	Summary of Common (>=5%) Non-serious Adverse Events by System Organ Class and Preferred Term (Number of Participants and Occurrences) (Part 2 NHL)	Report for: Part 2 NHL, (Summarize for Total). Include baseline values.	SAC
3.0710	All Treated	AE3	Summary of Common (>=5%) Drug-Related Grade 2-4 Adverse Events by Overall Frequency (Part 1)	Report for: Part 1, (Summarize by ascending dose level, Total). Include baseline values.	SAC [A]
3.0711	All Treated	AE3	Summary of Common (>=5%) Drug-Related Grade 2-4 Adverse Events by Overall Frequency (Part 2 MM)	Report for: Part 2 MM, (Summarize: only for 3.4 MM). Include baseline values.	SAC [A]

CONFIDENTIAL

BMA117159

Safety: Tables					
No.	Population	IDSL / Example Shell	Title	Programming Notes	Deliverable [Priority]
3.0712	All Treated	AE3	Summary of Common (>=5%) Drug-Related Grade 2-4 Adverse Events by Overall Frequency (All Treated MM)	Report for: All Treated MM, (Summarize for Total). Include baseline values.	SAC [A]
3.0713	All Treated	AE3	Summary of Common (>=5%) Drug-Related Grade 2-4 Adverse Events by Overall Frequency (Part 2 NHL)	Report for: Part 2 NHL, (Summarize for Total). Include baseline values.	SAC
3.0010	All Treated	AE13	Adverse Event Overview (Part 1)	Report for: Part 1, (Summarize: by ascending dose level, Total).	SAC [A]
3.0011	All Treated	AE13	Adverse Event Overview (Part 2 MM)	Report for: Part 2 MM, (Summarize: only for 3.4 MM)	SAC [A]
3.0012	All Treated	AE13	Adverse Event Overview (All Treated MM)	Report for: All Treated MM, (Summarize: Total).	SAC [A]
3.0013	All Treated	AE13	Adverse Event Overview (Part 2 NHL)	Report for: Part 2 NHL, (Summarize: only for 3.4 NHL)	SAC
3.0100	All Treated	AE1	Summary of Adverse Events of Maximum Grade 3 or Higher by System Organ Class and Preferred Term (Part 1)	Report for: Part 1, (Summarize: by ascending dose level, Total).	SAC [A]

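### The common Grade 2-4 adverse-event tables stop at Grade 4, so a subject whose only record of a term is fatal is not counted, and one such case can take the term below the 5% cut in those tables

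*SAP*

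**What the plan says.** SAP section 16.12.8 (Safety Tables) lists two series of frequency-cut tables with a closed grade range. Tables 3.0790-3.0793 cover all causalities, for example "Summary of Common (>=5%) Grade 2-4 Adverse Events by Overall Frequency (Part 2 MM"). Tables 3.0710-3.0713 cover drug-related events, for example "Summary of Common (>=5%) Drug-Related Grade 2-4 Adverse Events by Overall Frequency (Part 2 MM"). Their programming notes give the population and columns and, for the drug-related series, a request for baseline values. None mentions Grade 5.

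Section 8.1 fixes the scale: "Adverse events (AEs) will be graded according to the CTCAE, Version 4.0". For the summary by maximum grade it adds a counting rule for the preferred-term row: "Subjects experiencing the same AE preferred term several times with different grades will only be counted once with the maximum grade". It does not describe the Grade 2-4 tables or say why they stop at 4.

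The plan's other severity-restricted summary of all events has no upper limit: "Summary of Adverse Events of Maximum Grade 3 or Higher by System Organ Class and Preferred Term (Part 1"), Table 3.0100, with 3.0101-3.0103 for the other populations.

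The end-of-study plan, section 4.1.4, repeats 3.0793 ("Grade 2-4 Adverse Events by Overall Frequency (Part 2 NHL")) and 3.0713 for lymphoma with the same range.

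**The concern.** The plan expects fatal events: the section 8.1 overview counts fatal SAEs and related fatal SAEs. A closed upper limit drops a subject from the count because the outcome was worse, which is the wrong direction for a table meant to pick out the more severe common events. A reader would expect a Grade 2 and above count to contain the Grade 3 and above count. As written, a term with one fatal case and nothing else shows one subject in 3.0101 and none in 3.0791.

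Safety is the primary objective (section 2.2) and the cohorts are small, so one subject can decide whether a term is listed. What is at stake is the accuracy of these particular displays.

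**Working it through.** The plan gives no figure to reproduce here. The check is a direct count.

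**Inputs**
- Part 2 MM: "Subjects with relapsed/refractory MM (up to 40 subjects"), section 2.3, so N = 40 at most.
- Part 2 NHL: at most 10, section 2.3.
- Part 1: 30 originally planned, later exceeded, section 2.3. N = 30 is used as the stated figure.
- All Treated MM: 30 + 40 = 70, an assumption, because Part 1 went beyond 30.
- Cut: 5%, unrounded. Section 8.1 says "no rounding for the percentage will be used in terms of 5% threshold" for the non-serious table only; the same is assumed here.
- Fatal grade: 5, assumed, because the SAP names the scale without printing it.

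**Formula.** Let k be the smallest count with k/N ≥ 0.05. If one of those k subjects has only a fatal record of the term, the Grade 2-4 count is k − 1, and the percentage is (k − 1)/N.

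| Cohort | N | k | k/N | (k − 1)/N |
|---|---|---|---|---|
| Part 2 MM | 40 | 2 | 5.0% | 2.5% |
| Part 2 NHL | 10 | 1 | 10.0% | 0.0% |
| Part 1 | 30 | 2 | 6.7% | 3.3% |
| All Treated MM | 70 | 4 | 5.7% | 4.3% |

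None of the last-column values reaches 5%, even rounded to a whole percent.

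**Reach of the result.** By construction the term is lost only when it sits at the minimum count. With three cases in 40, one of them fatal only, 3/40 = 7.5% becomes 2/40 = 5.0%: the term stays listed and only its count is low.

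**Which subjects are lost.** There are two cases.
1. The only record of the term is Grade 5. The subject is outside Grade 2-4 under any counting rule.
2. The subject has a separate Grade 2-4 record of the same term as well as a Grade 5 record. The subject is lost if the maximum-grade rule of section 8.1 is applied, and stays if the filter works on records. The SAP does not say which applies to these tables.

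**Where fatal events still appear**
- Main list: 3.0780-3.0783 use the same shell, 5% cut and populations with no grade limit, so the 2/40 example is listed in 3.0781. Tables 3.0030-3.0033 and 3.0060-3.0063 show all and drug-related events by maximum grade with no cut. SAE tables and fatal SAE listings also carry them.
- End-of-study lymphoma list: 3.0783 and 3.0103 are not repeated. The frequency-cut tables kept are 3.0793, 3.0713 and the non-serious 3.0693, and all three leave out fatal events. Tables 3.0033 and 3.0063 are kept and still show them.

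**The case against.** The strongest reply is that each title states its range and the table would report exactly that range. Nothing in section 8.1 promises a Grade 2 or higher table or requires nesting with 3.0100-3.0103. That stands: this is a correctly labelled subset with a poorly chosen limit, and the plan does not contradict itself. But the label gives no reason for leaving out the worst grade.

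A second reply is that the same information is elsewhere. This also stands, and it limits the point. A reader might infer that fatal events vanish from common-event reporting, or that severe drug-related events cannot be seen. The documents do not support either: in the main list 3.0780-3.0783 keep the term, and 3.0060-3.0063 show drug-related Grades 3, 4 and 5 without a cut.

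A third reply is that the counting mechanism is not fixed. A reader might infer that every subject who progresses from Grade 3 to Grade 5 drops out. That does not follow, because the maximum-grade rule is written for the by-maximum-grade summary and these titles do not say maximum grade. Likewise, if common were judged on all-grade frequency, the term would stay and only its count would be too low. Neither reading rescues the subject whose only record is fatal.

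**Conclusion.** The concern holds as a minor display defect. Eight tables in the main list, two of them repeated at end of study, leave out any subject whose only record of a term is fatal. If the maximum-grade rule is applied, they also lose a subject with an additional Grade 2-4 record. A term at the minimum count then falls below the cut (2/40 to 1/40; 1/10 to 0/10).

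This assumes that Grade 5 is the fatal grade and that the 5% cut is taken on the Grade 2-4 frequency. The examples are hypothetical: they need a fatal case in a term at the threshold.

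It would be tempting to conclude that the primary safety assessment is biased. The documents do not support that. No death count or primary safety conclusion depends on these tables. The gap is widest in the end-of-study lymphoma list, where no frequency-cut table includes fatal events, although the by-maximum-grade tables do.

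**What to change.** Change the selection and titles of 3.0790-3.0793 and 3.0710-3.0713 to Grade 2 or higher. Apply the 5% cut after Grade 5 events are included, and state in the programming notes that each subject is counted once per preferred term. Make the same change to 3.0793 and 3.0713 in section 4.1.4 of the end-of-study plan. The 2/40 and 1/10 examples are then listed at 5.0% and 10.0%, and every subject in 3.0100-3.0103 also falls within the Grade 2 or higher range.

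If Grade 5 is left out on purpose, say so and give the reason in a footnote.

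The cost is one selection condition, eight titles and a short programming note, with the two end-of-study entries updated to match. No new data are needed.
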